Appendix 5 International Classification of Retinopathy of Prematurity (ROP)

The International Classification of ROP is a general agreement on staging of active disease.

- Stage I. A thin demarcation line develops between the vascularized region of the retina and the avascular zone.
- Stage II. This line develops into a ridge protruding into the vitreous, in which there is histologic evidence for an arteriovenous shunt.
- Stage III. Extraretinal fibrovascular proliferation occurs with the ridge. Neovascular tufts may be found just posterior to the ridge.
- Stage IV. Fibrosis and scarring occur as the neovascularization extends into the vitreous. Traction occurs on the retina, resulting in retinal detachment.
- Plus disease Noted when vessels posterior to the ridge become dilated and tortuous (eg, stage III+)

Gomella, TL, et al. Neonatology: Management, Procedures, On-Call Problems, Diseases and Drugs, Appleton & Langes, 1994, p.438.

Statistical Analysis Plan

A Multicenter, Randomized, Open-Label, Controlled Trial
to Assess the Safety and Tolerability of Lucinactant for Inhalation
in Preterm Neonates 26 to 28 Weeks PMA

Protocol Number: 03-CL-1401

SAP Version: Original

13 May 2015

A Multicenter, Randomized, Open-Label, Controlled Trial to Assess the Safety and Tolerability of Lucinactant for Inhalation in Preterm Neonates 26 to 28 Weeks PMA

Statistical Analysis Plan

Author/Project Biostatistician

[name]
Biostatistician
Discovery Laboratories, Inc.

Date

By signing below, I have read through the entire statistical analysis plan and agree to implement the plan.

[name]
Executive Director, Biostatistics and Data Management
Discovery Laboratories, Inc.

Date

[name]
Senior Vice President, Chief Development Officer
Discovery Laboratories, Inc.

Date

EXECUTIVE SUMMARY

The primary objective of this study is to evaluate the safety and tolerability of lucinactant for inhalation, administered as an aerosol in 4 escalating doses to a preterm, neonatal population receiving nasal continuous airway pressure (nCPAP) for respiratory distress syndrome (RDS), compared to neonates receiving nCPAP alone.

This is a multicenter, randomized, open-label, controlled study comparing lucinactant for inhalation administered with nCPAP to treatment with nCPAP alone for the treatment of RDS in 26 to 28 completed weeks post-menstrual age (PMA) preterm infants. Infants will be randomized into 1 of 4 sequential dose groups, with an allowed repeat dose if the repeat dose criterion is met. Reconstituted lyophilized lucinactant (reconstituted with sterile water for injection) will be aerosolized by the investigational device, ADS, using the capillary aerosol generator and introduced into the nCPAP circuit. Those infants randomized to the control arm will continue to receive nCPAP alone.

Exposure, defined as the emitted dose, is the amount of lucinactant that is delivered at the connection to the patient interface by the ADS at a constant rate of flow. The theoretical inhaled dose – the fraction of the aerosolized lucinactant that the infant is exposed to that is likely to be inhaled – is estimated by product of: 1) the aerosol concentration, 2) the minute ventilation of the infant, and 3) the administration time of the aerosol.

Study Group	Treatment Assignment	Number of Subjects
Dosing Group I	Active Arm : 50 mg TPL/kg Delivered over 30 minutes in conjunction with nCPAP 1 repeat dose allowed if repeat dosing criterion met	n=8
	Control Arm : Continuous nCPAP	n=8
Dosing Group II	Active Arm : 75 mg TPL/kg Delivered over 45 minutes in conjunction with nCPAP 1 repeat dose allowed if repeat dosing criterion met	n=8
	Control Arm : Continuous nCPAP	n=8
Dosing Group III	Active Arm : 100 mg TPL/kg Delivered over 60 minutes in conjunction with nCPAP 1 repeat dose allowed if repeat dosing criterion met	n=8
	Control Arm : Continuous nCPAP	n=8
Dosing Group IV	Active Arm : 150 mg TPL/kg Delivered over 90 minutes in conjunction with nCPAP 1 repeat dose allowed if repeat dosing criterion met	n=8
	Control Arm : Continuous nCPAP	n=8

Note: TPL = Total Phospholipids

Dosing Group I will complete study dosing and all active subjects will complete 72 hour safety assessments and procedures before the Safety Review Committee (SRC) review. The SRC will complete their review of all available Dosing Group I safety data (to include study-related adverse events [AEs], serious adverse events [SAEs], and additional safety endpoints) before recommending advancing enrollment to additional dosing groups. If the SRC concludes there are no safety concerns that would preclude proceeding to the next higher dose, dosing will commence in Dosing Group II. Likewise, the SRC will review the safety and tolerability of this dose and each succeeding dose, with dosing proceeding in the next dosing group if the SRC determines there are no safety concerns.

Repeat dosing will be allowed in each dosing group. Subjects meeting the repeat dosing criterion will receive an additional treatment of the same dose. Repeat dosing will be allowed between 2 and 24 hours after completion of the initial dose.

Subjects will be followed for safety evaluations (including, but not limited to, AEs and concomitant medications) until the subject is 36 weeks PMA or is discharged. Descriptive statistics (number of subjects, percent, mean, standard deviation, median, minimum, maximum) will be presented by treatment group, defined as each of the active doses (n = 8; 32 subjects total) and the all controls combined (n = 32). A final visit will occur at 36 weeks PMA or at the time of discharge or withdrawal (whichever occurs first) for all subjects.

Key safety and tolerability endpoints in the study include:

- AEs and ADEs (including peri-dosing events and nasal excoriations)
- Air leak (especially pneumothorax and pneumomediastinum)
- Survival
- Use of respiratory support and supplemental oxygen
- Complications of prematurity
- Assessments of the following:
 - a) Arterial carbon dioxide (PCO₂)
 - b) Serum electrolyte measurements
 - c) Vital signs
 - d) Gastric liquid volume
 - e) Oxygen saturations (SpO₂)
- Chest radiography prior to intubation, if such a procedure does not delay or compromise the emergent care of the subject

A peri-dosing event is defined as an adverse event with an onset time ≤ 2 hours from the time of initiating administration of lucinactant for inhalation

Efficacy endpoints (exploratory objective) in the study include:

- Incidence of bronchopulmonary dysplasia (BPD) at 36 weeks PMA
- Rate of survival without BPD at 36 weeks PMA
- Technical performance of the ADS
- Worsening respiratory status either during or after exposure to lucinactant for inhalation
- Physiological parameters (eg, FiO₂, PCO₂)

The statistical analysis of both the primary and secondary safety and tolerability objectives will be based on all randomized preterm neonates in the study. In addition, data from all evaluable preterm neonates will be analyzed for efficacy signals as an exploratory endpoint. As this is an open-label study with no hypothesis testing, no adjustments for *p*-values are required or employed.

TABLE OF CONTENTS

EXECUTIVE SUMMARY	3
1 OVERVIEW.....	9
1.1 BACKGROUND.....	9
1.1.1 Treatment of Neonatal Respiratory Distress Syndrome	9
1.1.2 Development of Aerosolized Device for Lucinactant Delivery	10
1.2 OBJECTIVES	11
1.2.1 Primary Objective	11
1.2.2 Secondary Objective	11
1.2.3 Safety Evaluations	11
1.2.4 Exploratory Efficacy Objective	12
1.3 HYPOTHESES.....	13
2 INVESTIGATIONAL PLAN	14
2.1 STUDY POPULATION	14
2.1.1 Inclusion criteria	14
2.1.2 Exclusion Criteria	14
2.2 STUDY DESIGN AND RANDOMIZATION.....	15
2.2.1 Treatment Groups	16
2.2.2 Repeat Dosing	16
2.2.3 Sample Size Justification	17
2.2.4 Study Schedule	18
3 STUDY SUBJECT CHARACTERISTICS.....	19
3.1 DEMOGRAPHICS AND BASELINE CHARACTERISTICS	19
3.1.1 Demographics	19
3.1.2 Birth and Maternal History	19
3.2 SUBJECT DISPOSITION	19
3.3 STUDY AND CONCOMITANT MEDICATION.....	20
3.3.1 Compliance	20
3.3.2 Number of Doses	20
3.3.3 Previous and Concomitant Medication	20

SAP	Statistical analysis plan
SOC	System Organ Class
SRC	Safety Review Committee
TPL	Total phospholipids
UADE	Unanticipated adverse device effect
WHO	World Health Organization

1 OVERVIEW

This statistical analysis plan (SAP) provides a comprehensive and detailed description of strategy, rationale, and statistical techniques to be used to assess safety and tolerability in the 03-CL-1401 study of lucinactant for inhalation in preterm neonates. The purpose of the SAP is to ensure the credibility of the study findings by pre-specifying the statistical approaches to the analysis of study data prior to database lock. This SAP provides additional details concerning the statistical analyses that are outlined in the protocol.

1.1 BACKGROUND

1.1.1 Treatment of Neonatal Respiratory Distress Syndrome

Surfactant treatment has reduced mortality and morbidity in newborns with respiratory distress syndrome (RDS). Intratracheal⁽¹⁾ instillation of exogenous surfactant is a standard treatment for the treatment of RDS, and the benefits of surfactant treatment, specifically early surfactant treatment, are well established⁽²⁾. However, instillation of surfactant into the lung requires endotracheal intubation, an invasive procedure that has potential deleterious effects.

Efforts by neonatologists to avoid endotracheal intubation to reduce the volutrauma and barotrauma associated with airway inflation and deflation have focused on the use of nasal continuous positive airway pressure (nCPAP), reserving intubation and surfactant administration for the most severely ill neonates.

The use of nCPAP in preterm neonates with RDS has become widely accepted⁽³⁾ and national guidelines (American Association for Respiratory Care)⁽⁴⁾ exist for treatment of respiratory distress in preterm newborns. These guidelines outline several patient interface devices that can be used to deliver continuous airway pressure such as nasal masks, short bi-nasal prongs, and nasopharyngeal tubes. It has been demonstrated that nCPAP is effective in increasing functional residual capacity by stabilizing and improving alveolar function⁽⁵⁾ and in dilating the larynx⁽⁶⁾. Devices that generate and deliver nCPAP, including patient interfaces such as nasal prongs, are specifically designed, manufactured, and registered for use in neonates.

While the use of nCPAP in preterm infants is common, studies of nCPAP alone, including a meta-analysis of prophylactic nCPAP for preventing morbidity and mortality in very preterm neonates, have not shown a clear benefit of this approach⁽⁷⁾. A large, multicenter, randomized clinical study (N = 610) was performed to compare the effects of nCPAP alone versus intermittent mechanical ventilation (IMV) for very preterm neonates at birth. This study showed that in the nCPAP group, the need for surfactant therapy was half of that compared to subjects in

the intubation group, and death or oxygen treatment at day 28 after birth was less frequent ($p = 0.006$). However, there were no differences in survival or oxygen therapy at 36 weeks, overall mortality, days of respiratory support, oxygen treatment, hospital stay, or other secondary outcomes. Of note, a higher rate of pneumothorax in the nCPAP group compared to the intubation group (9% versus 3%) was observed, and over 50% of infants in the nCPAP group required endotracheal intubation⁽⁸⁾. Other studies comparing nCPAP to endotracheal intubation and surfactant administration have also demonstrated a relatively high rate of endotracheal intubation in the group receiving nCPAP⁽⁹⁾.

1.1.2 Development of Aerosolized Device for Lucinactant Delivery

Discovery Laboratories, Inc. (Discovery) has developed a capillary aerosol generator (CAG) device to aerosolize lucinactant (Aerosurf[®], lucinactant for inhalation). Pre-clinical studies using the CAG technology in spontaneously breathing preterm lambs receiving aerosolized lucinactant have demonstrated significant improvements in lung mechanics and gas exchange compared with lambs receiving CPAP alone. In addition, pilot clinical studies using aerosolized lucinactant in neonates with RDS, as well as in adults with asthma and cystic fibrosis, have preliminarily demonstrated that aerosolized lucinactant is generally safe and well-tolerated. Data from a large neonatal database support the assumption that prophylactic use of aerosolized surfactant and nCPAP may reduce the need for intubation by 36% in neonates with a birth weight of 1001 to 1500 grams.⁽¹⁾

Because aerosolized surfactant is preferentially delivered to the ventilated parts of the lungs, it is essential to provide appropriate ventilatory support during aerosol delivery. Distribution of aerosol in the lungs has been limited by the technical constraints of currently available aerosol generators and system configurations. Compared with the endotracheal instillation surfactant administration route, efforts to aerosolize surfactants in clinical models have been largely unsuccessful because of the highly inefficient and limited dose delivery compared with the bolus administration route of currently available aerosol generators^(10,11). However, the CAG technology may allow for administration of aerosolized lucinactant to be deposited in the lungs of preterm neonates in potentially sufficient quantities to affect a therapeutic response analogous to that of endotracheal instillation surfactant administration. An investigational device, Aerosurf Delivery System (ADS), utilizing the CAG has been developed and provides a high-density surfactant aerosol output (20 $\mu\text{l}/\text{sec}$), with an appropriate particle size (2 to 3 microns mass median aerodynamic diameter [MMAD]). The ADS will be used in the current study to aerosolize lucinactant.

The purpose of this study is to investigate the safety and tolerability of lucinactant for inhalation, administered as an aerosol, in 4 escalating dose concentrations with a potential repeat dose to a preterm, neonatal population, 26 to 28 completed weeks post-menstrual age (PMA), receiving nCPAP for RDS, in comparison with neonates receiving nCPAP alone. The results of this phase 2a study will provide an assessment of the safety and tolerability of the doses studied, and will assist in the selection of doses for further clinical investigation.

1.2 OBJECTIVES

1.2.1 Primary Objective

The primary objective of this study is to evaluate the safety and tolerability of aerosolized surfactant, specifically lucinactant for inhalation (30 mg TPL/ml), administered in escalating theoretical inhaled doses of 50, 75, 100, and 150 mg TPL/kg to preterm neonates 26 to 28 completed weeks (28 weeks 6 days) PMA who are receiving nCPAP for RDS, compared to neonates receiving nCPAP alone. The primary objective of this study will be assessed based on safety evaluations, including adverse events (AEs) and serious adverse events (SAEs), and tolerability of the device, reported from the time of randomization until 36 weeks PMA.

1.2.2 Secondary Objective

The secondary objective of this study is to determine the maximum tolerated dose of lucinactant for inhalation as determined by the safety evaluations, including AEs and SAEs, obtained within each dosing group.

1.2.3 Safety Evaluations

The following measures are to be documented in the electronic case report form (eCRF) in accordance with timings outlined in study schedule:

1. Survival (date and time of death if applicable)
2. AEs, including ADEs
 - To include: nasal excoriations by examination (≥ 24 hours to ≤ 7 days following aerosol exposure) and evidence of lung air leak (especially pneumothorax)
 - To be categorized as a peri-dosing events if onset of event is ≤ 24 hours from the time of initiating administration of lucinactant for inhalation
3. Signs consistent with worsening respiratory status
4. Concomitant medications
5. Use of respiratory support and supplemental oxygen to include:

- Need for endotracheal intubation and mechanical ventilation
 - Need for intermittent positive pressure breaths using inflating pressures above the set CPAP pressure administered manually or mechanically through any patient interface
6. nCPAP and fraction of inspired oxygen (FiO₂) requirements
 7. Complications of prematurity (ie, IVH, periventricular leukomalacia [PVL], pulmonary hemorrhage, NEC, patent ductus arteriosus [PDA], sepsis, ROP, BPD)
 8. Physical examinations
 9. Tolerability of lucinactant for inhalation
 10. Incidence leading to withdrawal from study
 11. Incidence of air leak
 12. Assessments of the following:
 - a) PCO₂
 - b) Serum electrolyte measurements
 - c) Body weight
 - d) Vital signs
 - e) Gastric liquid volume
 - f) Defecation
 - g) Oxygen (O₂) saturation, as determined by pulse oximetry (SpO₂)
 - h) Chest radiography, as applicable

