3.3 Safety Evaluations

The following measures are to be documented in the electronic case report form (eCRF) in accordance with timings outlined in Appendix 2 and Section 7:

1. Survival (date and time of death if applicable)

2. AEs, including ADEs
 - To include: nasal excoriations by examination (≥ 24 hours to ≤ 7 days following aerosol exposure) and evidence of lung air leak (especially pneumothorax) (Section 7.1.8)
 - To be categorized as a peri-dosing events if onset of event is ≤ 2 hours from the time of initiating administration of lucinactant for inhalation [Section 9])
3. Signs consistent with worsening respiratory status (Section 7.5)
4. Concomitant medications (Section 7.3)
5. Use of respiratory support and supplemental oxygen (Section 7.6), to include:
 - Need for endotracheal intubation and mechanical ventilation
 - Need for intermittent positive pressure breaths using inflating pressures above the set CPAP pressure administered manually or mechanically through any patient interface
 - nCPAP and fraction of inspired oxygen (FiO₂) requirements (Section 5.4.1), (Section 7.6.2)
6. Complications of prematurity (ie, IVH, periventricular leukomalacia [PVL], pulmonary hemorrhage, NEC, patent ductus arteriosus [PDA], sepsis, ROP, BPD)
7. Physical examinations (Section 7.1.6)
8. Tolerability of lucinactant for inhalation
9. Incidence leading to withdrawal from study
10. Incidence of air leak
11. Assessments of the following:
 - a) PCO₂ (Section 7.1.5)
 - b) Serum electrolyte measurements (Section 7.1.7)
 - c) Body weight (Section 7.1.2)
 - d) Vital signs (Section 7.1.1)
 - e) Gastric liquid volume (Section 7.1.9)
 - f) Defecation (Section 7.1.10)
 - g) Oxygen (O₂) saturation, as determined by pulse oximetry (SpO₂) (Section 7.1.3)
 - h) Chest radiography, as applicable (Section 7.1.8)

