8.2 Primary Observation Period

The following will be documented for each randomized subject during the Primary Observation Period of the study (≤ 48 hours after randomization [T_0]):

1. Date and time (T_0) of randomization and the study dosing group assignment (Section 5.2.2)
2. The date and time of the initiation and completion of aerosol delivery (Section 5)
3. All AEs, including ADEs (Section 9)
Peri-dosing events (defined as an AE with an onset time ≤ 2 hours from the time of initiating administration of lucinactant for inhalation) may include but not be limited to:
 - Bradycardia (as noted by HR < 100 bpm for ≥ 20 seconds) (Section 7.1.1)
 - Desaturation (as noted by O₂ saturation $< 80\%$ for ≥ 20 seconds) (Section 7.1.3)
 - Gagging/regurgitation
 - Apnea (central, obstructive, or combined) (Section 7.1.1)
 - Pallor
 - Complications related to placement of bi-nasal prongs (bleeding, apparent obstruction of the nares, bi-nasal prongs occlusion requiring removal and replacement, nasal irritation).
4. Respiratory support and supplemental oxygen as outlined in Section 7.6
5. nCPAP settings (Section 5.4), (Section 7.6)
6. FiO₂ values (Section 7.1.4)
7. Signs and symptoms consistent with worsening of respiratory status (Section 7.5)
8. Vital signs and SpO₂ (Section 7.1.1, Section 7.1.3)
9. PCO₂ values (Section 7.1.5)
10. Chest radiograph, as applicable (Section 7.1.8)
11. Gastric liquid volume (Section 7.1.9)
12. Serum electrolytes (Section 7.1.7)
13. Defecation (initial 24 hours following randomization) (Section 7.1.10)
14. Concomitant medications (Section 7.3)
15. Technical performance of the device (Section 5.1.4)
16. The use of pacifiers

8.3 Extended Observation Period:

The following assessments are to be performed during the Extended Observation Period of the study (> 48 hours to ≤ 7 days after date of randomization). Daily measurements are to be obtained as close to 0800 as possible.

1. Assessment and documentation of respiratory support and supplemental oxygen (Section 7.6)
2. Signs and symptoms consistent with worsening of respiratory status (Section 7.5)
3. Vital signs (Section 7.1.1)
4. SpO₂ (Section 7.1.3)
5. Chest radiograph, as applicable (Section 7.1.8)
6. Incidence of AEs, including ADEs (Section 9)
7. Concomitant medications (Section 7.3)

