- ⁸ Serum electrolytes are to be evaluated 24 hours from randomization (± 6 hours) (Section 7.1.7)
- ⁹ Gastric liquid volume will be assessed 30 minutes (± 15 minutes) following completion of lucinactant for inhalation administration. Enteral feedings are to be held during and ≥ 1 hour following completion of lucinactant for inhalation administration (Section 7.1.9).
- ¹⁰ Peri-dosing events are defined as any adverse event with an onset time ≤ 2 hours from the time of initiating administration of lucinactant for inhalation

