¹⁰ Peri-dosing events are defined as any AE with an onset time ≤ 2 hours from the time of initiating study treatment.

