6.4.1 Peri-Dosing AEs

The incidence of peri-dosing events (bradycardia, desaturation, and vomiting) will be summarized. In addition, the incidence of complications related to the placement of bi-nasal prongs (bleeding, apparent obstruction to the nares, occlusion of the prongs, nasal irritation, and other) will be summarized. Peri-dosing events and complications related to the placement of the prongs will also be summarized with all adverse events.

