11 LIST OF TABLES

Table	Title
1.1	Subject Disposition – Study Populations – All Subjects
1.2	Subject Disposition – Study Completion/Termination Status – All Subjects
1.3	Subject Disposition – Protocol Deviations/Violations – All Subjects
2.1	Subject Demographics – Intent-to-Treat Population
2.2	Medical Information – Maternal History – Intent-to-Treat Population
2.3	Medical Information – Birth History – Intent-to-Treat Population
3.1	Concomitant Medications – Safety Population
3.2	Number of Treatments Received – Safety Population
4.1.1	Exploratory Efficacy Analysis – Early Worsening of Respiratory Status Criteria – Intent-to-Treat Population
4.1.2	Exploratory Efficacy Analysis – Late Worsening of Respiratory Status Criteria – Intent-to-Treat Population
4.2	Exploratory Efficacy Analysis – BPD and Survival Without BPD at 36 Weeks PMA – Intent-to-Treat Population
4.3	Exploratory Efficacy Analysis – Time until Intubation for Mechanical Ventilation – Intent-to-Treat Population
4.4	Exploratory Efficacy Analysis – Time until Any Intubation – Intent-to-Treat Population
5.1	Investigational Device – Technical Performance – Safety Population
5.2	Investigational Device – Early Termination of Treatment – Safety Population
6.1	Peri-Dosing Adverse Events – Safety Population
6.2	Air Leak – Safety Population
6.3.1	Treatment-Emergent Adverse Events by System Organ Class and Preferred Term – Safety Population
6.3.2	Treatment-Emergent Adverse Events by System Organ Class, Preferred Term, and Severity – Safety Population
6.3.3	Treatment-Emergent Adverse Events by System Organ Class, Preferred Term, and Relationship – Safety Population
6.3.4	Treatment-Emergent Adverse Events by Severity and Relationship to Study Drug – Safety Population
6.3.5	Treatment-Emergent Adverse Events in Descending Order by Total Active Group – Safety Population
6.4.1	Serious Adverse Events by Preferred Term Displayed in Descending Order by Total Active Group – Safety Population
6.5.1	Adverse Device Effects by Treatment Group – Safety Population
6.6	All-Cause Mortality – Safety Population

- 7.1.1 Clinical Assessments – Vital Signs – Body Temperature – Observed Values and Change from Baseline – Safety Population
- 7.1.2 Clinical Assessments – Vital Signs – Respiration Rate – Observed Values and Change from Baseline – Safety Population
- 7.1.3 Clinical Assessments – Vital Signs – Heart Rate – Observed Values and Change from Baseline – Safety Population

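### SAP 1.2.3 gives a 24-hour peri-dosing window where five other places give 2 hours, and SAP 6.4.1 restates no window and leaves apnea out of the peri-dosing summary

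*SAP*

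**What the plan says.** **Window.** SAP 1.2.3 states: "To be categorized as a peri-dosing events if onset of event is ≤ 24 hours from the time of initiating administration". The parallel sentence in Protocol 3.3 is nearly identical except for the number: "To be categorized as a peri-dosing events if onset of event is ≤ 2 hours from the time of initiating administration". Protocol 8.2 uses the same 2-hour limit, and the last footnote to Protocol Appendix 2 says "Peri-dosing events are defined as any adverse event with an onset time ≤ 2 hours". Within the SAP itself, the Executive Summary says "A peri-dosing event is defined as an adverse event with an onset time ≤ 2 hours", and the last footnote to the schedule in SAP 2.2.4 says "Peri-dosing events are defined as any AE with an onset time ≤ 2 hours from the time of initiating study treatment".

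**Events counted.** SAP 6.4.1 specifies the analysis: "The incidence of peri-dosing events (bradycardia, desaturation, and vomiting) will be summarized". It adds a summary of bi-nasal prong complications and gives no onset limit. The output is Table 6.1, titled "Peri-Dosing Adverse Events – Safety Population", also without a window.

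**Protocol lists.** Appendix 1 defines AEs related to dosing as four items: bradycardia, desaturation, sustained apnea and prong complications. Protocol 8.2 includes apnea among its examples of peri-dosing events. Protocol 9 numbers four AEs of special interest: bradycardia, desaturation, sustained apnea and air leak.

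**The concern.** Safety and tolerability are the primary objective, and SAP 1.2.2 derives the maximum tolerated dose from the safety evaluations in each dosing group. The SAP has no hypothesis tests, so in arms of 8 what each table counts is the result. Table 6.1 is the one listed output meant to isolate events close to aerosol administration.

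Two things undermine it. First, a programmer who works from SAP 6.4.1 must look elsewhere for the window and will find two answers in the same SAP. Second, SAP 2.2.4 defines a peri-dosing event as any AE in the window, while SAP 6.4.1 narrows the summary to a short list that omits apnea.

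The bradycardia and desaturation rows do not fully stand in for apnea. Protocol 9 requires each of those events to last at least 20 seconds. Sustained apnea must itself last at least 20 seconds, but no minimum duration is set for the accompanying fall in heart rate or saturation, and the need for positive-pressure breaths alone can satisfy the definition. An apnea with only a brief fall, or one that qualifies through positive-pressure breaths, would have no row in Table 6.1.

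**Working it through.** **1. Every statement of the window**

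| Place | Onset limit from start of administration |
|---|---|
| Protocol 3.3 | 2 h |
| Protocol 8.2 | 2 h |
| Protocol Appendix 2, footnote 10 | 2 h |
| SAP Executive Summary | 2 h |
| SAP 2.2.4, footnote 10 | 2 h |
| SAP 1.2.3 | 24 h |
| SAP 6.4.1 and Table 6.1 title | none stated |

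Five places agree and one differs. The ratio is 24/2 = 12 and the difference is 24 − 2 = 22 hours.

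**2. Share of each window during which aerosol is running**

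The dose durations are those of Protocol 5.2.2. Share = duration / window, with windows of 120 and 1440 minutes.

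| Dosing group | Duration | Share of 2 h | Share of 24 h |
|---|---|---|---|
| I | 30 min | 30/120 = 25.0% | 30/1440 = 2.1% |
| II | 45 min | 45/120 = 37.5% | 45/1440 = 3.1% |
| III | 60 min | 60/120 = 50.0% | 60/1440 = 4.2% |
| IV | 90 min | 90/120 = 75.0% | 90/1440 = 6.3% |

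**3. Overlap with the repeat dose**

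The protocol summary and the SAP Executive Summary allow a repeat dose from 2 to 24 hours after the initial dose is completed. Measured from the start of the initial dose, the earliest repeat is at 0.5 + 2 = 2.5 h (Group I) to 1.5 + 2 = 3.5 h (Group IV). A 2-hour window on the initial dose therefore closes before any repeat can begin. A 24-hour window takes in most of the repeat-dose interval, so events around the two administrations would be mixed.

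**4. Event lists compared**

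| Protocol item | Named in SAP 6.4.1 or 6.4.2? |
|---|---|
| Bradycardia (Appendix 1 and Section 9) | Yes, 6.4.1 |
| Desaturation (Appendix 1 and Section 9) | Yes, 6.4.1 |
| Prong complications (Appendix 1) | Yes, 6.4.1 |
| Air leak (Section 9) | Yes, 6.4.2 |
| Sustained apnea (Appendix 1 and Section 9) | **No** |

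SAP 6.4.1 covers 3 of the 4 Appendix 1 items. SAP 6.4.1 and 6.4.2 together cover 3 of the 4 numbered AEs of special interest. Apnea is the missing item in both.

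**5. Where apnea does appear in the SAP**

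- General AE tables (6.4.3): by preferred term and system organ class.
- Complications of prematurity (6.5.8): incidence over the study.
- Worsening respiratory status (4.3.2, Tables 4.1.1 and 4.1.2): classed early or late by time from birth.

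None of these is timed from the start of aerosol.

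**The case against.** The strongest reply is that this is a harmless slip. SAP 1.2.3 sits in the objectives section, nearly copies Protocol 3.3, and defers to the study schedule for timings; that schedule says 2 hours. Both places where the SAP formally defines the term also say 2 hours. This makes 2 hours very probably the intended value. It does not remove the second rule from a document whose stated purpose is to fix the analysis before database lock, and the section that specifies Table 6.1 does not settle the matter.

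It can also be said that a 2-hour window is itself mostly post-aerosol in Groups I and II (25.0% and 37.5% aerosol time). That is right, so the shares above show a difference of degree and do not show that any result would change.

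On apnea, the reply is that the events are not lost. They appear in the three SAP outputs listed above, early termination of aerosol is tabulated and listed, and the safety review committee sees all AEs and, under Protocol 13.2, reviews the Appendix 1 category that contains apnea. All of this stands. The point is therefore confined to the SAP's listed tables, none of which shows apnea against time from dosing.

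Finally, the peri-dosing list in Protocol 8.2 is explicitly non-exhaustive. Against it SAP 6.4.1 also lacks pallor, and has vomiting where the protocol has gagging or regurgitation. Apnea is the sole omission only against Appendix 1 and the numbered AEs of special interest.

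**Conclusion.** The point holds. The SAP contains two onset rules for a listed safety endpoint, 12-fold apart, and the section that specifies the table does not say which applies. That section also leaves out one of the four AEs the protocol classes as related to dosing, although the SAP's own definition covers any AE in the window.

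The conflict and the omission are read directly from the text and need no assumption. The practical consequence of the window conflict depends on 24 hours actually being programmed. The consequence for apnea follows if SAP 6.4.1 is implemented as listed. The documents give no event rates, so no effect on counts is claimed. The correction should be made before database lock; neither the committee's access to apnea data nor the general AE tables are affected.

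**What to change.** - In SAP 1.2.3, change 24 hours to 2 hours, to agree with the other five places.
- In SAP 6.4.1, state that a peri-dosing event is one with onset within 2 hours of the start of an administration, initial or repeat. No passage spells out the per-administration reading, but it follows from a window that runs from initiating administration.
- In Table 6.1, add a line for any AE with onset in the window and a named row for apnea beside bradycardia, desaturation and vomiting. Keep the prong-complication summary as it is.
- Optional: tabulate initial and repeat doses separately, and name rows for pallor and for gagging or regurgitation.

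The cost is wording in two SAP sections plus one line and one row in one table. AE onset times (Protocol 9) and aerosol start times (Protocol 8.2) are already recorded, and Protocol 5.2.5 applies the initial-dose procedures to the repeat dose, so nothing new is collected.
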